**Aim 2c: Correlation of Biomarker and Self-Reported Alcohol Consumption:**

CONFIDENTIAL

This material is the property of the NYU School of Medicine and Langone Medical Center. Do not disclose or use except as authorized in writing by the study sponsor

For this substudy, data from subjects in both arms (N=50 in phase 1) will be pooled as a single cohort to assess the performance of %CDT and the %CDT-GGT combination as a marker of heavy alcohol use. We will determine the correlation between serum biomarker values and self-reported alcohol intake ascertained using the timeline follow-back (TLFB) method (within the Form 90), which is reliable, validated, and widely used in addictions research. Correlations between the measures will be assessed and inform the second phase of study.

- I. We will measure the correlation between biomarker levels and self-reported alcohol consumption using the Timeline Followback method of obtaining (a) 30-day average alcohol intake, and (b) 7-day alcohol intake. We hypothesize that biomarker levels will be correlated with alcohol intake for both periods of time.
- II. We will measure the correlation between changes in biomarker levels and changes in alcohol intake. We hypothesize that changes in alcohol intake will be correlated to the associated changes in biomarker levels.
- III. We will compare the performance of biomarkers in subjects for whom CDT has been shown to have higher diagnostic accuracy (males, low BMI, non-smoker, non-cirrhotic liver) to subjects having at least one characteristic previously found to lower the accuracy of CDT (women, high BMI, smokers, cirrhotic liver).

We will calculate correlations using Pearson product-moment coefficients for continuous non-skewed parameters or the Spearman's rank correlations for non-continuous variables, as required. To reduce the effect of baseline variation and to allow each subject to be evaluated in relationship to his own drinking status, and initial blood level, CDT and GGT will be expressed at each treatment week as a percentage of their baseline level. Therefore, at each treatment evaluation, every individual's levels would either decrease or increase. A multivariate approach to repeated-measures ANOVA will be conducted for the biomarker levels using the percentage of baseline at the three treatment evaluations (Months 3, 6, and 12) as the dependent units for analysis in comparing the outcome groups. Multiple sensitivity analyses will be conducted to address missing data.

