**Sample Size - Performance of Biomarkers as an objective measure of Alcohol Consumption:**

Based on the literature, the correlation between the CDT level and self-reported alcohol consumption using validated, reliable methods among alcohol dependent patients ranges from approximately  $r = .35$  to  $r = .60$ . However, the relationship between CDT levels and alcohol intake may be influenced by age, gender, BMI, cirrhosis, smoking status, flushing, and other factors, such that the correlation among these subgroups groups is less (although, typically not powered to reach statistical significance). Because of potential inter-individual variation, measuring the change in CDT from an individual's baseline as a continuous variable appears to improve performance. Recent studies have also suggested that the combination of CDT and gamma-glutamyl transpeptidase (GGT), via the equation  $[0.8*\ln(GGT) + 1.3*\ln(CDT)]$ , has higher diagnostic sensitivity and stronger correlation with the actual amount of alcohol consumed than either of the parent compounds alone; in one study the correlation of CDT-GGT was  $r = .76$ ;  $p < .001$ .

We will determine the correlation between serum biomarker values and self-reported alcohol intake ascertained using the timeline followback method, which is reliable, validated, and widely used in addictions research. For our sample size calculation, the null hypothesis is there is no correlation between CDT value and reported consumption. The alternative hypothesis uses the values found in literature. The sample size calculation for each of these studies uses a type I error of 0.05. The correlation between alcohol intake and CDT level with a sample size 49, a correlation coefficient 0.39 can be detected with power 0.8. Correlation between change in CDT to change in drinking with a sample size 61, a correlation coefficient 0.35 can be detected with power 0.8. All sample size calculations are done by PASS (Power Analysis and Sample Size) 2008. See also Table 3. The first phase of study, N=50, has the approximate power required to test the primary hypotheses. We will also pool the results of Phase 1 subjects with those enrolled in phase 2.

Author	Study Results		N required
	r	p	
Mikkelsen	0.39	0.006	49
Hietala	0.59	<.001	20
Anton (all) ^	0.35	<.05	61
Anton (outliers removed) ^	0.54	0.001	24
Kim (flushers only) #	0.608	<.01	18

CONFIDENTIAL

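### Aim 2c analyses CDT and GGT as raw percent of baseline with no log scale or baseline covariate, which costs power and leaves the result dependent on baseline

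*Combined protocol and SAP*

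**What the plan says.** Section 7.2.2, Aim 2c, pools both arms to "assess the performance of %CDT and the %CDT-GGT combination as a marker of heavy alcohol use". The reason given for the analysis scale is "To reduce the effect of baseline variation and to allow each subject to be evaluated in relationship to his own drinking status", and the scale itself is set by "CDT and GGT will be expressed at each treatment week as a percentage of their baseline level". The model follows: "A multivariate approach to repeated-measures ANOVA will be conducted for the biomarker levels using the percentage of baseline at the three treatment evaluations", with these percentages serving "as the dependent units for analysis in comparing the outcome groups". Those groups are not defined in Aim 2c and are not said to be the randomised arms. No log transform, baseline covariate or rank alternative is named for this ANOVA.

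For the correlations, the plan uses "Pearson product-moment coefficients for continuous non-skewed parameters or the Spearman's rank correlations for non-continuous variables, as required". Skewed continuous values are assigned to neither method, although Aim 2 of the same section expects several endpoints to be non-normal.

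Section 7.1 refers to "the combination of CDT and gamma-glutamyl transpeptidase (GGT), via the equation" 0.8·ln(GGT) + 1.3·ln(CDT). That index is already logarithmic. Aim 2c names only CDT and GGT for the percentage scale and does not say how change in the index is to be expressed.

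**The concern.** Dividing by baseline replaces a positive dependence on baseline with a negative one. A subject whose baseline sample happened to be high tends to show a low percentage, and the reverse. The scale is also asymmetric: a halving reads 50 and a doubling reads 200, so a few subjects with low baseline values can dominate a mean. An ANOVA on this scale with no covariate uses the data less well than it could.

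CDT and GGT are the plan's laboratory measures of drinking in an open-label trial where the other drinking measures are self-reported. Aim 2 says that their performance will inform the design of phase 2. At stake are the sensitivity of these analyses, how within-group means are read, and the validity of any comparison between groups that start at different levels.

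**Working it through.** **Inputs from the documents.** Percent of baseline at months 3, 6 and 12 (Aim 2c); N=50 pooled in phase 1 (Aim 2c), that is 25 per group if split evenly; 125 per arm in phase 2, two-sided alpha 0.05, and N=61 for r=0.35 at power 0.80 (Section 7.1 and Table 3).

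**Assumptions.** The documents give no SD and no baseline-to-follow-up correlation for either marker. I take log-normal values with log-SD s from 0.6 to 1.0 (0.4 as a low-spread case) and correlation r of 0.6 to 0.8, one follow-up visit, and a true 20% fall, ln(0.8) = −0.223.

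**1. The plan's own figure.** No power is stated for the ANOVA. The change correlation can be checked with power = Φ{[atanh(ρ) + ρ/(2(N−1))]·√(N−3) − 1.96}. For ρ=0.35 and N=61: (0.3654 + 0.0029)·7.616 − 1.96 = 0.845, power 80%. The plan's 61 is reproduced. At N=50: (0.3654 + 0.0036)·6.856 − 1.96 = 0.570, power 72%.

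**2. Dependence on baseline.** The correlation of the log ratio with log baseline is −√((1−r)/2): −0.45 at r=0.6 and −0.32 at r=0.8. The rank correlation of percent of baseline with baseline is −0.43 and −0.30. For the unadjusted follow-up level it is +0.58 and +0.79.

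**3. Skewness.** With w = 2s²(1−r), skewness is (e^w + 2)·√(e^w − 1). At s=0.8, r=0.6: w=0.512 and skewness 3.0. At s=0.4 it is about 0.8 to 1.2, which is moderate.

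**4. Within-group mean when the median does not change.** The mean is 100·exp(s²(1−r)). At s=0.6, r=0.8: 100·e^0.072 = 107%. At s=1.0, r=0.6: 100·e^0.40 = 149%. At s=0.8, r=0.6, a true 20% median fall gives 80·e^0.256 = 103%.

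**5. Power of a two-group contrast** (simulated, per cent):

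| n per group | s | r | Percent of baseline | Log ratio, no covariate | Log level, log baseline as covariate |
|---|---|---|---|---|---|
| 125 | 0.8 | 0.6 | 58 | 69 | 78 |
| 125 | 0.6 | 0.6 | 86 | 90 | 95 |
| 125 | 1.0 | 0.8 | 71 | 78 | 82 |
| 125 | 1.0 | 0.6 | 37 | 50 | 59 |
| 125 | 0.4 | 0.6 | over 99 | over 99 | over 99 |
| 25 | 0.8 | 0.6 | 15 | 19 | 21–23 |

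Closed-form check of the first row:
- Covariate-adjusted residual SD 0.8·√(1−0.36) = 0.64; SE 0.64·√(2/125) = 0.081; 0.223/0.081 − 1.96 = 0.80; power 79%.
- Log-ratio SD 0.8·√0.8 = 0.716; SE 0.0905; power 69%.

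Of the 20-point gap, 78 − 69 = 9 points come from the missing covariate and 69 − 58 = 11 from the raw ratio.

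**6. Type I error.** With equal baselines, percent of baseline stays near 5%. Next, let the groups differ by 0.5 SD at baseline while follow-up depends on a subject's own baseline in the same way in both groups. At s=0.8, r=0.6 and 125 per group, type I error is about 33–35% for percent of baseline, 43% for the log ratio without covariate and 5% for log level adjusted for log baseline. The covariate, not the log alone, removes this.

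**7. Change correlation (hypothesis II).** With true r=0.35 on the log scale, s of 0.4–1.0 and baseline-to-follow-up correlation 0.5–0.7, Pearson on percent of baseline has 62–79% power at N=61 against about 80% on log change. At N=50 it has 55–70% against about 71–72%.

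**8. The index.** Halving both markers always changes it by (0.8 + 1.3)·ln(0.5) = −1.456. As a percentage of its own baseline, that same change would read 39%, 67%, 77% or 82% for illustrative GGT/CDT baselines of 20/1, 60/2.5, 200/5 and 600/10.

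**The case against.** Several points on the other side stand.

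- **Stated purpose.** The plan says it aims to reduce the effect of baseline, not to remove it. In absolute size the rank correlation falls from 0.58–0.79 to 0.30–0.43, so the purpose is partly met.
- **Source of the loss.** Between about a third and 60% of the power gap comes from the absent covariate, not from the ratio.
- **Assumed spread.** The size of the loss rests on spreads that the documents do not give, and at 125 per group with log-SD 0.4 it disappears. CDT, the lead marker, may vary less than GGT.
- **Simplified model.** The calculation uses one visit and arm-sized groups, whereas the plan has three visits and undefined groups. The powers show direction and rough size; they are not the power of the planned test.
- **Existing alternatives.** Aim 2 allows signed-rank tests for within-group change and adjustment for confounders. Spearman, if chosen for skewed data, would give the same result on either scale. None of these is tied to the Aim 2c ANOVA, and Spearman is assigned only to non-continuous variables.

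A reader might infer two stronger points that the documents do not support. One is that a treatment contrast would show a false rise. The mean above 100% is a within-group feature; it affects groups with equal baselines alike and cancels in the contrast. The other is that the plan divides the logarithmic index by its baseline. The plan does not say so; the index's change scale is simply not stated.

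**Conclusion.** The concern holds as a point of efficiency and specification. Raw percent of baseline without a covariate is a weaker choice than log level adjusted for log baseline, by about 20 percentage points of power in the middle of the assumed range at 125 per group and by almost nothing when spread is low. Within-group mean percentages of about 107–149% can arise with no change in the median and should not be read as a rise.

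Between groups, validity is at risk only if their baselines differ, which cannot be excluded while the outcome groups are undefined. The one-in-three error rate also assumes that both groups regress toward a common level. Groups with permanently different levels would raise a separate question, which is another reason to define them.

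The analysis is secondary and exploratory, and no stated sample size rests on this ANOVA. It should be changed because the better method uses data already planned, not because the trial's main conclusions depend on it.

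**What to change.** In Section 7.2.2, Aim 2c:

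- Replace percent of baseline with ln(CDT) and ln(GGT) at months 3, 6 and 12 as the dependent variables, with the log baseline value as covariate. Report back-transformed geometric mean ratios with confidence intervals.
- Define the outcome groups.
- For hypothesis II, correlate the log-ratio of the marker with change in intake, and say which coefficient applies to skewed continuous variables.
- State that change in the CDT-GGT index is follow-up minus baseline, adjusted for the baseline index, and not a percentage.

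The cost is SAP wording only, with the same samples and assays. Results will read as geometric mean ratios instead of mean percentages.

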## Timeline of Study Procedures:

Week	0	1	4	8	12	16	20	24	28	32	36	40	44	48
Enrollment (ED) Consent, Capacity Assessment (UBACC), DSM Diagnostic Interview (Alcohol Use), History & Physical Exam, Demographics, Below Assessments, Labs (AST, ALT, GGT, hCG, Drug Screen, genetics, CDT,), XR-NTX Arm*: Psychosocial Assessment, Interview, Care Management intake, XR-NTX injection	X													
Research Visits (ED, ED Office Space) • Broad Range of Assessments: Alcohol and Substance Use, Health Status, Psychosocial (Housing, Legal, etc.), Quality of Life, Craving, Self-efficacy, Healthcare and Services Utilization, Adverse Events • Qualitative Assessments/Interview • Laboratory: Biomarker to Quantitate Drinking	X				X			X						X
Clinical Visits (Clinic or ED) Adverse Event Form Medical Management Note		X	X*	X*	X*	X*	X*	X	X^	X^	X^	X^	X^	
Pre-Injection Labs (as needed): AST,ALT,GGT, hCG, Drug Screen	X*		X*	X*	X*	X*	X*	X^	X^	X^	X^	X^	X^	
XR-NTX 380mg injection	X*		X*	X*	X*	X*	X*	X^	X^	X^	X^	X^	X^	
Subject Compensation	40	10	25*	25*	40	25*	25*	40	25^	25^	25^	25^	25^	40

Table 2: It is expected, particularly in this challenging cohort, that subjects will not be present for all clinical (and research) visits. The pragmatic study design allows considerable flexibility—allowing delayed and missed visits. Similarly, the timing of certain clinical services (e.g. psychosocial assessments and care management intakes) will vary because they depend on the availability of existing clinical staff. The window for subjects to receive XR-NTX injections will not close until the 48th week after subject enrollment. Key: [Green] is both arms; \*[Turquoise Blue] is intervention arm; ^[Grey-Blue] is intervention arm subjects that extend XR-NTX treatment.

CONFIDENTIAL

This material is the property of the NYU School of Medicine and Langone Medical Center. Do not disclose or use except as authorized in writing by the study sponsor

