Attachment 4: Schematic Diagram of Trial (also in Section 3.1)  
Attachment 5: Timeline of Study Procedures (also in Section 3.1)  
Attachment 6: Anticipated Study Timeline (also in Section 3.1)

It is expected, in this challenging cohort, that subjects will not be present for all clinical (and research) visits. The pragmatic study design allows considerable flexibility—allowing delayed and missed visits. The window for subjects to receive XR-NTX injections will close 52 weeks after enrollment. The schedule for research assessment visits is weeks 12, 24, and 48; the time-window during which these research assessments may be conducted will be extremely liberal. If a scheduled date has passed, we will perform a research assessment at the next available opportunity (up to 6 months after the 48 week visit). Research visits may be conducted up to 28 days prior to- or 90 days after- date in which research visits are due. The below described procedures are the “ideal” conditions that are not expected in this “real world” study. Non-completion of all procedures and deviation from intended schedule is expected and will not be considered protocol violations.

For the following study procedures, study investigators (PI/RA) will enter data directly into NYUMC-internal REDCap system for use on portable tablets or computers. NYUMC internal REDCap is HIPAA compliant and data will be stored on secure servers with access only to authorized study personnel. Any paper forms containing protected health information will be stored in a locked filing cabinet within the locked office of the PI. Data will be linked to the subjects using a unique identifier.

**Study Setting:** Research will be performed on the NYU School of Medicine campus and Bellevue Hospital Center by study investigators. Recruitment will take place in the Bellevue ED (inclusive of Department of Emergency Medicine clinical and nonclinical space to ensure privacy and to minimize disruption of ongoing ED care). Follow up visits will occur in the Bellevue ED, Bellevue ambulatory care clinic, or the Clinical and Translational Science Institute Clinical Research Center. If it is only possible for subjects to conduct research assessments off site (e.g. due to mobility or health), investigators may follow up with subjects off site.

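### Unless values are imputed, the repeated-measures ANOVA of CDT and GGT keeps only subjects with all three follow-up samples, in a trial that expects missed visits; a mixed model would use every follow-up sample that has a baseline

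*Combined protocol and SAP*

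**What the plan says.** Section 7.2.2, Aim 2c, expresses CDT and GGT as a percentage of each subject's own baseline. The stated reason is "To reduce the effect of baseline variation and to allow each subject to be evaluated in relationship to his own drinking status". It continues: "A multivariate approach to repeated-measures ANOVA will be conducted for the biomarker levels using the percentage of baseline at the three treatment evaluations", namely months 3, 6 and 12, "as the dependent units for analysis in comparing the outcome groups". The next sentence is the only missing-data provision for this analysis: "Multiple sensitivity analyses will be conducted to address missing data". No imputation or likelihood method is named.

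The groups are not defined. The same section says that for this substudy "data from subjects in both arms (N=50 in phase 1) will be pooled as a single cohort".

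On attendance, the note to Table 2 (Timeline of Study Procedures) expects that "subjects will not be present for all clinical (and research) visits". The opening of Section 6 adds: "Non-completion of all procedures and deviation from intended schedule is expected and will not be considered protocol violations". Section 11 expects attrition in severe alcohol use disorder. Section 13 accepts that research assessments may go uncompleted for some incarcerated subjects and leaves the handling of those missing data to discussion with the DSMB. Section 7.3 defines an all-randomized analysis population for the primary and secondary aims.

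**The concern.** The method does not suit the data that the protocol itself expects. A multivariate repeated-measures ANOVA needs the full set of three follow-up values, and here a baseline as well because the response is a percentage of it. A subject with blood drawn at months 3 and 6 but not at month 12 contributes nothing. Those samples would be collected, shipped and assayed, then left out of the main fit.

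Two things are at stake. One is precision in what appears to be the only comparison of CDT and GGT between groups over follow-up that Section 7.2.2 sets out. The other is the assumption about absence. A completers-only fit generally needs attendance to be unrelated to the outcome within groups. A likelihood fit allows absence to depend on values already observed, which is easier to defend where relapse or incarceration may lie behind a missed visit. A completers-only fit also sits awkwardly with the all-randomized population of Section 7.3.

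**Working it through.** **The plan's own figures.** None is given for the ANOVA. The nearest are the correlation sample sizes in Section 7.1: 49 for r = 0.39 and 61 for r = 0.35, with two-sided alpha 0.05 and power 0.80. Fisher's z gives N = ((1.960 + 0.842)/atanh(r))² + 3 = 49.3 and 61.8. Power at the stated sizes is 0.798 and 0.795. The stated figures are reproduced within rounding, and they concern correlations, not this analysis.

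**Inputs.** N = 50 (Aim 2c, phase 1) and three follow-up samples per subject come from the plan. Attendance per visit, p, is not given, so 70%, 80% and 90% are assumed. The pattern of misses is not given either, so it runs from independent to strongly clustered.

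**Formulas.**
- Independent misses: P(all three) = p³; P(at least one) = 1 − (1 − p)³.
- Clustered misses: a probit model with latent correlation r between visits. With c = Φ⁻¹(p) and g(u) = Φ((c + √r·u)/√(1 − r)), P(all three) is the mean of g(u)³ over standard normal u, and P(at least one) is 1 minus the mean of (1 − g(u))³.
- Collected follow-up samples left unused: 1 − P(all three)/p, since 3p samples per subject are collected and 3·P(all three) are used.

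Worked case, p = 0.7, independent: 0.7³ = 0.343, so about 17 of 50 subjects are complete. Collected: 3 × 50 × 0.7 = 105 samples. Used: 3 × 50 × 0.343 = 51. Unused: 1 − 0.343/0.7 = 51%.

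**Results** (each cell: 70% / 80% / 90% attendance).

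| Misses | All three | At least one | Complete, of 50 | Samples unused |
|---|---|---|---|---|
| Independent | 34 / 51 / 73% | 97 / 99 / 99.9% | 17 / 26 / 36 | 51 / 36 / 19% |
| Latent correlation 0.5 | 47 / 61 / 78% | 90 / 95 / 98% | 23 / 31 / 39 | 33 / 24 / 13% |
| Latent correlation 0.95 | 63 / 75 / 87% | 77 / 85 / 93% | 32 / 37 / 43 | 10 / 7 / 4% |
| Same subjects miss every visit | 70 / 80 / 90% | 70 / 80 / 90% | 35 / 40 / 45 | 0% |

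**Check on the method.** In one simulated dataset of 50 subjects with 70% attendance and 114 follow-up samples, a multivariate fit kept 22 subjects (66 samples). A mixed model used all 114 samples, from 49 subjects.

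**Power at phase 1 size, illustrative only.** Assumptions: 25 per group, a lognormal marker with log SD 0.5, a group shift of 0.3 log SD, correlation between measurements 0.3 to 0.7, attendance missing completely at random (independent or latent correlation 0.5), and group known for everyone. On the plan's percent scale, power is 0.08 to 0.27 for complete cases and 0.14 to 0.34 with all available samples. Under stronger clustering (latent correlation 0.8 to 0.95, correlation between measurements 0.5) the gain is about 1 to 4 percentage points.

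**The case against.** **The plan already addresses missing data.** In part. It promises sensitivity analyses, and Aim 2 proposes triangulating data sources. But unnamed sensitivity analyses do not change the main fit, and no other source replaces a missing blood sample. It is fair to say that a complete-case main fit is nowhere stated; it follows from the named method plus silence on imputation. If imputation was intended, it still has to be written down. The repeated-measures analysis mentioned under Aim 2 concerns healthcare use and expenditures.

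**Make-up visits will fill the gaps.** Late assessments and the ED alert reduce the loss, but the protocol still expects missed visits. Section 13 also allows research assessments by phone, which yield no blood.

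**The loss may be small.** This stands. Loss to follow-up and incarceration can make misses cluster in the same subjects. A reader might infer that most subjects are bound to be lost, or that nearly everyone would still have at least one sample. The documents support neither as a fixed fact, because they give no attendance rate and no pattern.

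**Group membership may itself depend on attendance.** This also stands. The groups are undefined in a cohort that pools the arms. If they are defined by drinking measured at the same research visits, a subject who misses visits may be unclassifiable, and a mixed model recovers less.

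**The analysis is a phase 1 exercise.** Largely right. A reader might carry the loss over to 300 subjects and infer large power losses in the definitive trial. Section 7.1 does say "We will also pool the results of Phase 1 subjects with those enrolled in phase 2", but in the correlation sample-size text and without mention of the ANOVA, while Aim 2c describes the substudy at 50.

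**Conclusion.** The point holds with limited stakes. As written, and unless values are imputed, the main fit uses only subjects with a baseline and all three follow-up samples. At an assumed 70% to 90% attendance, that leaves unused 51% to 19% of collected follow-up samples under independent misses, 33% to 13% at latent correlation 0.5, 10% to 4% at 0.95, and none if the same subjects miss every visit. The mechanism is certain; the size rests on assumed attendance and clustering.

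A reader might go further and infer that the biomarker sample sizes fail, or that percent of baseline is itself the error. Neither is supported. The correlations and their sample sizes do not depend on this ANOVA, and the plan gives a reason for self-referencing each marker. A log-ratio response or a baseline covariate is an optional refinement, separate from the missing-visit problem. The analysis is secondary and exploratory, and power at 50 subjects is low under either method. The change is worth making because it is cheap and the missingness is foreseen.

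**What to change.** In Section 7.2.2, Aim 2c:

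1. Make the main analysis a linear mixed model fitted by likelihood to all available month 3, 6 and 12 values that have a baseline. Include group, visit and group-by-visit, with an unstructured covariance and a small-sample degrees-of-freedom correction such as Kenward-Roger.
2. Keep the complete-case multivariate ANOVA as one of the promised sensitivity analyses. Name at least one other that departs from missing at random, for example delta-adjusted multiple imputation.
3. State which groups are compared. The full gain applies if membership is known for every subject, as with the randomized arms. If groups are defined by drinking at the same visits, say how subjects with missed visits are classified and expect a smaller gain.

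The cost is SAP wording and a little more analysis work, with no new visits, samples or patients. The downside is reliance on missing at random, which the sensitivity analyses should probe.
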